### Disease Characteristics:

Time from initial diagnosis to randomization

Primary Tumor Side

Histopathological Type at Initial Diagnosis

Histological Grade at Initial Diagnosis

Stage IV Disease at Initial Diagnosis (Yes/No)

Time from Metastatic / Locally Recurrent Disease to randomization

Disease Status at Registration

Prior Surgery for Breast cancer and Prior Anti-Tumor Therapy

### **10.3 Medical History**

Not Applicable.

### **10.4 Study Drugs Administration**

Number of cycles, Duration of treatment, Cumulative dose (for Afatinib only) and Relative dose intensity (RDI) will be summarized by treatment for the safety population.

The relative dose intensity will be additionally presented categorized (i.e., number and percentage of subjects with relative dose intensity of <60%, 60-<80%, 80-<90%, 90-<110%, ≥110%).

The number and percentage of subjects with dose interruptions/discontinuations or reduced (Afatinib only), along with their respective reasons will be summarized.

For Afatinib, the compliance will be summarized by visit following this calculation :

$$\text{Compliance (\%)} = \left[ \frac{\text{Number of tabs taken}}{\text{Sum of each sub-administration duration in a visit}} \right] \times 100$$

When the total number of tabs taken does not equal the number of tabs dispensed minus the number of tabs returned, the reasons will also be summarized.

## 10.5 Efficacy Analyses

Efficacy data for the primary endpoint and the secondary endpoints will be analyzed for the ITT population. Sensitivity analyses and subgroup analyses will be conducted as appropriate. Summaries and figures of the efficacy endpoints will be generated by randomization group.

### 10.5.1 Progression Free Survival (PFS) - Primary Endpoint

Progression-free survival will be summarized using Kaplan-Meier (KM) curves and compared between treatment arms using a stratified log-rank test, stratifying for Bone only disease (Yes vs. No) and by Prior neo/adjuvant hormonal therapy (Yes vs. No). The Kaplan-Meier estimate of the PFS survival distribution function will be computed for each treatment group using PROC LIFETEST with method=KM option in SAS. The results will also be plotted graphically (Kaplan-Meier curves) by each treatment arm. The plots will also display the number of subjects at risk at equidistant time points.

For each randomization group, the Kaplan-Meier estimates for the median PFS time, the first and third quartiles will be presented, along with approximate 95% confidence intervals (CI).

The effect of treatment on PFS will also be compared using a stratified Cox proportional hazards regression model using the stratification variables at randomization as strata. This model will generate estimates of the stratified treatment hazard ratio, respectively. Additional stratified Cox regression models might be employed to explore the effects of additional prognostic variables (considered as covariates in the model) on PFS. The hazard ratio with two-sided 95% confidence interval will be derived from the stratified Cox proportional hazards model using PROC PHREG with ties=EXACT option in the model.

A sensitivity analysis will be performed on Progression free survival to assess the robustness of the results. Therefore, subjects receiving any non-protocol anti-cancer therapy during the treatment period before an assessment of disease progression will be

censored on the last available assessment date prior to initiating medication or the date of surgery or radiotherapy.

### **10.5.2 Overall Survival (OS) – Secondary Endpoint**

The treatment groups will be compared using the stratified log-rank test and the survival curves will be estimated, together with corresponding summary statistics. The survival curves for each treatment group will be generated using the Kaplan-Meier methodology. The effect of treatment on OS will also be compared using a stratified Cox proportional hazards regression mode using the stratification variables at randomization as strata.

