2.1.2 Secondary Objectives

- To assess secondary measures of efficacy for afatinib administered in combination with letrozole and for letrozole alone.

Endpoints:

Overall survival (OS)

Objective Response rate (OR)

Time to tumor progression (TTP)

- To assess the safety and tolerability of afatinib administered in combination with letrozole and of letrozole alone.

Endpoint: overall safety profile

The patient enrolment was closed prematurely on 05 MAR 2016 due to the small number of patients randomized compared to what was initially planned as per the statistical analysis. The data collected for all the patients will be described per arm but no statistical comparison will be made. Therefore the primary and secondary objectives are not applicable. .

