- If the patients treated with the combination of afatinib and letrozole (arm B) discontinue the trial treatment (whatever the reason) before 30 November 2018, the patients from the other arm (arm A, letrozole alone) still on treatment will also be discontinued from the trial at the same time. They may continue receiving letrozole using commercial drug as standard of care according to their treating physician discretion.

[figure not shown]
- If the patients treated with afatinib and letrozole (arm B) have not discontinued the trial treatment by 30 November 2018, all patients currently on treatment in the trial (including the ones only treated by letrozole alone (arm A)) will be discontinued from the trial at that time. They may continue receiving their treatment if in alignment with their treating physician judgment as follows:
 - Patients in arm A: may continue receiving letrozole using commercial drug as standard of care according to their treating physician discretion.
 - Patients in arm B: may continue receiving afatinib in the context of an alternative drug supply outside the clinical trial as appropriate according to local legislation. Additionally, they may continue receiving letrozole using commercial drug as standard of care according to their treating physician discretion.
- Note; In case no alternative drug supply outside the clinical trial as appropriate according to local legislation can be put in place and the 2 patients in Arm B are still on treatment on 30 November 2018, the protocol and PICF will need to be revised again.

Once the patient is discontinued from trial treatment and has undergone the End of Treatment visit (see section 6.3), the patient will be permanently discontinued from the trial.

This trial also included an optional exploratory research component. This optional portion of the trial is a molecular profiling assay aimed to assess the relationship of antitumor activity with the expression of a few cell cycle-related proteins and other markers that may be identified in the future. (See section 2.3)

Patients participated in this trial even if they had chosen not to participate in the sample banking component.

Figure 1 : Trial Scheme - Patient Selection and Treatment

* As described in section 3-Trial Design (IN ADDITION)

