6.2 Trial Participation and Discontinuation

Once trial treatment is discontinued (both letrozole and afatinib) regardless of the reason, patients will be discontinued from the trial and will be followed and treated as per local clinical practice. If the patient withdraws from trial participation (consent withdrawn from trial, lost to follow-up, investigator's decision), no further trial procedures are performed, and no additional data will be collected. Medical care of the patient is not affected if the patient chooses to leave the trial at anytime.

Please refer to section 3-Trial Design (IN ADDITION) regarding the decision to discontinue the patients from the trial at the latest on 30 November 2018 and the conditions of this discontinuation.

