6.3 Schedule of Procedures

All screening and baseline evaluations had to be completed prior to initiating trial treatments. Adherence to the schedule of assessments is required and visits should be planned accordingly. In the event a visit is missed because of an unforeseeable event, then the missed visit should be scheduled for the next day.

Prior to undergoing any trial specific procedures not considered standard practice by the institution, patients had to read and sign the consent form. All trial procedures are detailed in the Schedule of Activities table presented below.

According to the information reported in section 3-Trial Design (IN ADDITION) regarding the decision to discontinue the patients from the trial at the latest on 30 November 2018, the information reported in this section is applicable until 30 November 2018. After that date, the patients will be followed by their physician as per standard of care and the assessments will be performed as per local practice.

Table 9 : Schedule of activities

Protocol Activities	Pre-screening	Screening ¹ 28 days prior randomization	Treatment Period ²	End of treatment ³
Signed ICF ⁴	X			
Local determination of ER/HER2	X			
Tumor sample to central lab.	X			
Medical, surgical, disease history		X		
Signs and symptoms		X		
SAFETY			q4w	
Physical exam / Vital signs / PS		X	X	X
Review of adverse events		X	X	X
Hematology / Blood chemistry		X ^{5, 6}	X ⁶	X ⁶
LVEF		X within 42 days	X ⁷ q12w	X
TREATMENT			q4w	
Letrozole / Afatinib : Dispensation / Accountability			X	
EFFICACY			q12w	
Disease assessment		X	X	
Survival / Anticancer therapy				

¹¹ Pre-screening / Screening starts once the subject has signed the PICF.

² Visits are scheduled every 4 weeks +/- 3 days during treatment phase.

³ End of Treatment visit must be scheduled as close as possible to 30 days post last intake of any study drug or on 30 November 2018 whichever occurs first.

⁴ There is no window for obtaining the signed ICF. Study specific screening assessments not considered standard practice by the institution may start once the PICF has been obtained.

⁵ At screening only, Creatinine clearance will be assessed to check eligibility if serum creatinine $\geq 1.5 \times$ ULN.

⁶ During treatment phase, blood tests must be obtained up to 5 days prior to the visit and will assess the following parameters :

Hematology: Hemoglobin, Absolute Neutrophils Count (ANC), Platelets.

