### **3. STUDY DESIGN**

This phase II, multicenter, multinational, open-label, parallel group, randomized study will compare a two-drug regimen of letrozole plus afatinib (BIBW2292) to letrozole alone in the first line treatment of ER+, HER2 negative postmenopausal Advanced Breast Cancer women with low ER expression.

Randomization is stratified by Bone only disease (Yes vs. No) and by Prior neo/adjuvant hormonal therapy (Yes vs. No). Eligible subjects will be randomly assigned in a 1:1 ratio to either:

**Arm A: Continuous regimen of oral letrozole 2.5 mg daily** until progression of disease or any other study treatment discontinuation criteria.

OR

**Arm B: Continuous regimen of oral letrozole 2.5 mg daily plus oral afatinib 30 mg daily** until progression of disease or any other study treatment discontinuation criteria.

Once the subject is discontinued from study treatment and has undergone the End of Treatment visit, the subject will enter into the follow-up phase.

This study also includes an optional exploratory research component. This optional portion is a molecular profiling assay aimed to assess the relationship of antitumor activity with the expression of selected cell cycle-related proteins and other markers that may be identified in the future. Subjects may participate in this study even if they choose not to participate in the sample banking component.

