**Overall Survival (OS)**

Overall survival (OS) is defined as the time from randomization to the time of death from any cause. Subjects who are alive at the end of the follow-up period, or are lost to follow-up during the study, will be censored at the last date known alive.

Duration of OS is defined as the time from randomization until death (or censoring if no death). It is defined as:

$$OS = \text{Date of Death/Censor} - \text{Date of Randomization} + 1$$

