### 11.3 Planned Figures

Title	Population	Description
Progression-Free Survival	ITT	Kaplan-Meier plot of Progression-Free Survival.
Overall Survival	ITT	Kaplan-Meier plot of Overall Survival.
Time to Progression	ITT	Kaplan-Meier plot of Time to Progression.

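### The SAP still plans Kaplan-Meier overall survival with a follow-up phase that the current protocol no longer has, so the curve is biased upward by an amount the documents do not fix

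*SAP*

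**What the plan says.** **SAP.** Section 3 says that after the End of Treatment visit "the subject will enter into the follow-up phase". Section 4.1 defines OS from randomization to death; patients alive or lost to follow-up "will be censored at the last date known alive". Section 10.5.2 plans a stratified log-rank test, a stratified Cox model and summary statistics, and states: "The survival curves for each treatment group will be generated using the Kaplan-Meier methodology". Section 11.1 lists an OS results table with the treatment comparison, and 11.3 lists a "Kaplan-Meier plot of Overall Survival".

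**Protocol.** Section 3 says that once treatment has stopped and the End of Treatment visit is done, "the patient will be permanently discontinued from the trial". Section 6.2 says that after treatment stops, for any reason, "patients will be discontinued from the trial and will be followed and treated as per local clinical practice". In Table 9 (section 6.3) the row "Survival / Anticancer therapy" has no visit marked, and there is no follow-up column. Section 8.6 ends the trial 30 days after the last intake or on 30 November 2018, whichever is first.

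On the status of OS, section 2.1.2 says: "The data collected for all the patients will be described per arm but no statistical comparison will be made". Its next sentence declares the primary and secondary objectives not applicable. Section 8 then sends the descriptive analyses to the SAP.

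**The concern.** Kaplan-Meier estimation needs patients censored at a given time to have the same outlook as those still observed. By default, treatment runs to RECIST progression (Protocol 5.3.3). With no later follow-up, a patient who stops for progression is last seen about a month afterwards. The patients who remain at risk are mostly those who have not progressed, so the curve drifts towards survival while progression-free and on treatment, yet is labelled overall survival.

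Dropping the tests would not cure this, because the per-arm curve and its median carry the bias. Follow-up may also be uneven: patients who left under earlier rules may have survival data that later leavers lack. The SAP has no rule for such a mixture, and its list of last-contact-date sources (section 6) names no survival contact explicitly. A reader of the OS figure could not tell how far to trust it.

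**Working it through.** **1. Design figure.** The documents give no OS design figure. The one event count is 127 PFS events (SAP 5.3). With HR = 9/14 = 0.643, two-sided alpha 0.10, power 80% and 1:1 allocation, events = 4(1.645 + 0.842)² / (ln 0.643)² = 126.7, so 127. The SAP's PFS assumptions are coherent and are used below.

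**2. Inputs from the documents.**
- Median PFS 9 or 14 months (SAP 5.2).
- Median OS 34 months, first-line letrozole (Protocol 1.2), or 24 months, the top of the range for metastatic disease (Protocol 1.1).
- Expected accrual 18 months (SAP 5.2). Enrolment closed 05 March 2016, which is 1,000 days or 32.9 months before 30 November 2018.
- Amendment 4.0 is dated 09 May 2016, 2.1 months after closure.
- The current protocol cites a paper dated 17 November 2016, so it was released at least 8.4 months after closure.
- Six patients were on treatment at the current amendment: two in Arm B, hence four in Arm A (Protocol 1.4).

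**3. Assumptions not in the documents.** Times are exponential. A share q = 5% or 10% of PFS events are deaths (5% in the dated scenarios). A patient without follow-up is censored 1 month after progression. Entry is uniform over the 18 months before closure.

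**4. Formulas.** Let λ = ln 2 / median PFS and μ = mean survival after progression. True OS is

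S(t) = e^(−λt) + (1−q)λ[e^(−t/μ) − e^(−λt)] / (λ − 1/μ),

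with μ solved so that S(median OS) = 0.5. If every patient is censored 1 month after progression, the death hazard seen by Kaplan-Meier settles at

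h = [qλ + (1−q)λk/μ] / [1 + (1−q)λk], where k = (e^a − 1)/a and a = λ − 1/μ,

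and the 24-month estimate is about e^(−24h).

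- *Largest excess:* PFS 14, OS 24, q = 5%. λ = 0.0495, μ = 9.79, k = 0.974. h = (0.00248 + 0.00468)/1.0458 = 0.00684, so the estimate is 0.85 against a true 0.50: excess 0.35.
- *Smallest excess under this censoring:* PFS 9, OS 34, q = 10%. λ = 0.0770, μ = 33.7, k = 1.024. h = (0.00770 + 0.00211)/1.071 = 0.00916, so the estimate is 0.80 against 0.65: excess about 0.16 before rounding.

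**5. Varying when follow-up stopped** (400,000 simulated patients per scenario). In the dated rows, patients already off treatment are censored at that date. Those still on treatment are observed to progression + 1 month or 30 November 2018.

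| Survival follow-up beyond treatment | 24-month OS, true 0.65–0.66 (median 34) | 24-month OS, true 0.50 (median 24) |
|---|---|---|
| None for any patient | 0.80–0.90 | 0.77–0.85 |
| Stopped at Amendment 4.0 (2.1 months after closure) | 0.78–0.81 | 0.69–0.71 |
| Stopped at current amendment, earliest date (8.4 months) | 0.70–0.73 | 0.57–0.60 |
| Stopped at current amendment, if 24–28 months after closure | no change | no change |

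In the last row the 36-month excess is at most 0.03.

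If instead only a share of patients lacks follow-up (median OS 34), the 24-month estimate is 0.65–0.68 at 10%, 0.66–0.70 at 25% and 0.69–0.75 at 50%.

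**6. Worst case at 36 months.** Take no follow-up for anyone, PFS median 9 months, q from 2% to 15% and median post-progression survival of 20 to 30 months. The excess runs from 0.647 − 0.517 = 0.13 to 0.870 − 0.463 = 0.41.

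**The case against.** **The protocol has already withdrawn OS.** It declares the objective not applicable, bars comparisons, and in sections 8.2 to 8.4 describes only baseline, treatment and safety summaries. This stands against the log-rank and Cox analyses, which now conflict with the protocol. It does not clearly remove the curve: section 2.1.2 still promises a per-arm description, section 8 hands descriptive analyses to the SAP, and a per-arm Kaplan-Meier curve is a description.

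**Most patients may have valid follow-up.** A reader might infer that every patient is censored a month after progression, and that the curve will therefore be 13 to 41 points too high at 36 months. The documents do not support that. Only six patients were on treatment at the current amendment; all others had already stopped, some or all perhaps under rules that included the follow-up phase in SAP 3. No text says which amendment removed survival follow-up. Patients stopped on 30 November 2018 while progression-free are censored by calendar date, not by progression. This objection stands in full against any fixed size.

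Nor should Protocol 5.1, where follow-up is said to have continued, be read as evidence about treated patients: it concerns patients randomized but never treated.

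**The OS method was sound for its design.** SAP 2.0 was aligned to a CRF of January 2014 and still carries 150 subjects, 127 events and comparative objectives. That is right: the fault is an SAP left behind by the protocol, and OS is one symptom.

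**Table 9 could be damaged in extraction.** Possible, but sections 3 and 6.2 say the same in prose.

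**Conclusion.** The conflict is real and the direction is clear. The SAP prescribes per-arm Kaplan-Meier OS, with comparisons, on a follow-up phase that the current protocol does not have. For patients who stop at progression without later follow-up, censoring is informative and the curve is biased upward.

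The size is not determinable. At 24 months it runs from about 0, if follow-up ended only with a current amendment released 24–28 months after enrolment closed, to about 0.35, if no patient was followed past treatment. The 13–41 points at 36 months is a worst case, not an expectation. All figures rest on exponential times, the assumed share of deaths among PFS events and the SAP's expected accrual; the documents give neither the number randomized nor the date of the current amendment.

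This is a reconciliation point on a secondary endpoint in a trial now reported descriptively. It should be corrected before the final analysis.

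**What to change.** In SAP 4.1, 10.5.2, 11.1 and 11.3, remove the OS log-rank and Cox comparisons. Then choose one of two options:

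- **(a)** Drop the OS curve and results table. Report the number of deaths by arm, with the death listing already planned in SAP 11.2.
- **(b)** If earlier protocol versions collected survival follow-up, cut OS data for all patients at the calendar date it ended, and report how many were followed beyond treatment. A common calendar cut does not depend on progression, so it removes this bias within its reach. The reach may be short: with 18 months of accrual, a cut at Amendment 4.0 gives at most 18 + 2.1 = 20.1 months.

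Under either option, correct the follow-up statement in SAP 3 and the last-contact-date sources in SAP 6, and state in Protocol 2.1.2 that OS after that date is not assessable.

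The cost is SAP wording, one clarifying protocol sentence and fewer outputs. The downside is a shorter OS description, or none. Option (b) keeps survival data that (a) would leave to a listing.

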### **10.5.3 Objective Response Rate (ORR) – Secondary Endpoint**

The objective response rates observed in the treatment groups will be compared adjusting for the stratification variables using the Cochran-Mantel-Haenszel (CMH) test.

A 95% CI will be calculated for each response rate. The best overall response outcome (CR/PR/SD/PD/Unevaluable [UE]) will be summarized and tabulated for the ITT population by treatment group and by the stratification variables using the Cochran-Mantel-Haenszel test as appropriate.

### **10.5.4 Time to Progression (TTP) – Secondary Endpoint**

The treatment groups will be compared using the stratified log-rank test and the survival curves will be estimated, together with corresponding summary statistics. The survival curves for each treatment group will be generated using the Kaplan-Meier methodology. The effect of treatment on TTP will also be compared using a stratified Cox proportional hazards regression mode using the stratification variables at randomization as strata.

## **10.6 Safety Analyses**

Safety analyses will be performed on the safety population.

### **10.6.1 Adverse Events**

The Medical Dictionary for Regulatory Activities (MedDRA version 16.0 or later) will be used to code all adverse events to a system organ class and a preferred term.

Subject incidence of Treatment Emergent Adverse Events will be tabulated by system organ class, preferred term and toxicity grade for all adverse event, serious, treatment-related, and serious treatment-related adverse events. Each of these outputs will include tabulation for each system organ class and preferred term as reported by the investigator based on Common Terminology Criteria for Adverse Events (CTCAE), version 4.0.

Summary tables will be provided separately for Treatment Emergent Adverse Events leading to investigational product discontinuation and Treatment Emergent Adverse Events leading to study withdrawal.

All AEs leading to deaths will be summarized (not only TEAEs). An AE will be considered as leading to death if it has a grade 5.

Detailed listings for all adverse events and listings and/or narratives will be provided for serious and significant adverse events, deaths, and treatment discontinued due to adverse events. A flag will be used to identify which adverse events are considered as treatment emergent or not.

